5.2 Study Endpoints

5.2.1 Primary Efficacy Endpoint

The primary efficacy endpoint is the mean grade of anterior chamber inflammation (ACI) in the study eye at Visit 5 (Postoperative Day 14). The ACI grade will be determined using either slit lamp biomicroscopy or a penlight with handheld magnification. The grading from each method will be combined into one ACI grade to be used as the primary endpoint, derived using the following table:

ACI Grade	Slit lamp	Penlight with handheld magnifying 20 diopter lens
0 = None	Grades 0 cells and flare	Grade 0
1 = Mild	Maximum of cells and flare Grade is 1	Grade 1
2 = Moderate	Maximum of cells and flare Grade is 2	Grade 2
3 = Severe	Maximum of cells and flare Grade is 3	Grade 3
4 = Very Severe	Maximum of cells and flare Grade is 4	Grade 4

5.2.2 Secondary Efficacy Endpoints

Secondary efficacy endpoints include the following:

- Mean grade of ACI at Visits 4 and 6 (Postoperative Days 7 and 28)
- Proportion of subjects with Grade 0, Grade 1, Grade 2, Grade 3, and Grade 4 converted ACI at each visit (Postoperative Days 7, 14, and 28)
- Presence/absence and total area, if present, of synechiae at each visit (Postoperative Days 7, 14, and 28)
- Presence/absence and total number, if present, of precipitates on the implant and cornea at each visit (Postoperative Days 7, 14, and 28)

5.2.3 Safety Endpoints

The safety endpoints include the following:

- Incidence of overall and specific adverse events (AEs)
- Type and incidence of AEs at each visit
- Change in IOP from baseline (Visit 2, Surgery/Randomization) to each visit
- Greatest IOP change from baseline - including the measurement at Visit 3 (Postoperative Day 1)
- Greatest IOP change from baseline - excluding the measurement at Visit 3 (Postoperative Day 1)
- Ocular signs (biomicroscopic examination of the lids, conjunctiva, cornea, anterior chamber without pupil dilation) at each visit

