5.1.6 Visit 6 (Postoperative Day 28, ±7 days; End of Treatment)

At Visit 6, the following assessments will be performed:

NOTE: All ocular assessments and VA will be performed bilaterally.

- AEs and changes in concomitant medications
- the unmasked designee must weigh both bottles of study drug and collect all used and unused study drug (both bottles)
- collect diaries

- ocular symptoms
- pediatric VA
- biomicroscopy
- IOP measurement

NOTE: Measurement of IOP must occur after the assessment of ocular symptoms, VA and biomicroscopy

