Subject's eyes meeting eligibility criteria at both Visit 1 (Screening) and Visit 2 (Surgery/Randomization) were randomized to receive study medication. If both eyes of a subject underwent routine, uncomplicated surgery at Visit 2 (Surgery/Randomization) and met eligibility criteria, the subject's right eye was considered the study eye. In the event that the subject required surgery on the contralateral eye at any time during the study, the fellow eye was treated with standard of care medication.

The subject will receive the first dose of study drug by the unmasked designee at the end of the surgery. Either the unmasked designee or the subject's parent/legal guardian will then administer 1 to 2 drops of study drug to the lower cul-de-sac of the study eye once in the evening on the day of surgery and then 4 times a day (QID), at approximately 4 hour intervals, beginning on the morning after surgery. QID dosing will continue until postoperative day 14, including dosing at appropriate time intervals on the day of a visit. Treatment will be tapered by altering the frequency of study drug dosing to twice a day (BID) during the interval between postoperative days 15 and 21. Treatment will be further tapered to once a day (QD) from postoperative day 22 until day 28, with the last dose being administered on the day prior to Visit 6 (Postoperative Day). No study drug doses were delivered after Visit 6, and subjects returned for post-dosing assessments at Visit 7 (Day 42) and Visit 8 (Day 90). Subjects then exited from the study.²⁸⁾

Schedule of Visits and Parameters

All study tasks should be performed by qualified study site personnel as indicated on the delegation of authority log under the supervision of the Principal Investigator. Furthermore, all ocular signs must be evaluated by an ophthalmologist.

PROCEDURE/ASSESSMENTS ¹	Visit 1 Screening	Visit 2 Surgery/Randomization /Begin Treatment	Visit 3 Follow-up	Visit 4 Follow-up	Visit 5 Follow-up	Visit 6 Follow-up/End Treatment	Visit 7 Follow-up	Visit 8 Study Exit
	Day -15 (±14 days)	Day 0 ²	Day 1 ³	Day 7 (±2 days)	Day 14 (±3 days)	Day 28 (±7 days)	Day 42 (±7 days)	Day 90 (±14 days)
Informed consent, assent (when applicable), and authorization as appropriate for local privacy regulations	X							
Demographic data	X							
Current and relevant medical and ocular history	X							
Ocular symptoms	X		X	X	X	X	X	X
VA assessment	X	X	X	X	X	X	X	X
Slit lamp (biomicroscopy or magnifying lens with penlight) ⁴	X	X	X	X	X	X	X	X

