IOP (Goldmann or equivalent) ⁴	X	X	X	X	X	X	X	X
Fundoscopy ⁵		X	X		X			X
Eligibility determination	X	X						
Randomization		X						
AEs ⁶ /Concomitant medications	X	X	X	X	X	X	X	X
Weigh study drug and inspect diaries		X	X	X	X	X		
Dispense study drug and diaries		X ⁷	X	X	X			
Collect study drug and diaries						X		
Exit subject								X

¹ All ophthalmic assessments will be performed bilaterally.

² Visit 2 must occur within 29 days of Visit 1. Screening and surgery cannot take place on the same day.

³ Visit 3 (postoperative day 1) should occur on the next calendar day post-surgery.

⁴ Every effort should be made to obtain slit lamp assessments and the assessment with the 20 dpt magnifying lens and penlight should only be performed if a slit lamp or handheld slit lamp examination cannot be performed. Once one of the methods has been chosen it should be employed throughout the study for each subject. IOP should also be measured with the same method throughout the study for each subject.

⁵ Fundoscopy will be performed bilaterally either at Visit 2 (surgery/randomization) or Visit 3 (postoperative day 1), at Visit 5 (postoperative day 14 ±3 days), and at Visit 8 (postoperative day 90 ±14 days).

⁶ Collection of AEs extends from the time the subject's parent/guardian signs informed consent until the last study visit.

⁷ The subject's parent/legal guardian will be trained with regard to the correct instillation of eye drops without using study drug prior to their administration of the initial dose.

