5.9 Dose Adjustment/Modifications

Treatment will be tapered from QID to BID during the interval between postoperative days 15 and 21. Treatment will be further tapered to QD from postoperative day 22 until day 28, with the last dose being administered on the day prior to Visit 6 (Postoperative Day 28).

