10.4.1 Treatment Emergent Adverse Events

Adverse events (AEs) are defined in Section 6.1 of the protocol and initiating collection of AEs is defined in Section 5.1.2 of the protocol. Adverse events will be coded using MedDRA dictionary version 13.0.

All AEs collected with start dates following the first administration of study drug or that worsen following the first administration of study drug are considered treatment-emergent adverse events (TEAE).

Adverse events with unknown severity will be counted as severe. Adverse events with unknown relationship to study drug will be counted as related to study drug. Adverse events with partial dates will have their start dates imputed. If the partial date is consistent with the first day of treatment, it will be imputed with this value; otherwise it will be imputed as the earliest possible date consistent with the partial data (first day of month/ year). If a start or end date are completely missing, then the date will be imputed with the dates of the first or last date of treatment, respectively.

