10.4.1.1 Incidence of Treatment-Emergent Adverse Events

Treatment emergent non-ocular AEs will be summarized using discrete summaries at the subject and event level by system organ class and preferred term for each treatment group. Treatment emergent ocular AEs will be summarized for treated study eyes and fellow eyes separately.

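### AE incidence by visit is a listed safety endpoint with no planned AE table by visit or period, and the pooled TEAE tables extend about 63 days past the planned last dose

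*SAP*

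**What the plan says.** SAP 5.2.3 and protocol 7.1.3 (also the protocol synopsis) list "Type and incidence of AEs at each visit" as a safety endpoint of its own, separate from the overall and specific incidence of AEs.

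The AE outputs are set out in SAP 10.4.1.1 to 10.4.1.7:

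- The main table, shown by arm: "Treatment emergent non-ocular AEs will be summarized using discrete summaries at the subject and event level by system organ class and preferred term". Events in the eye are shown separately for study and fellow eyes.
- Tables by relationship and by severity, with percentages out of the Safety sample.
- A table and listing of SAEs.
- Listings of TEAEs leading to discontinuation, of related TEAEs (with time to onset) and of deaths.

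Protocol 7.6.1 describes AE summaries of the same kind and adds none by visit.

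TEAEs are defined in SAP 10.4.1 as "All AEs collected with start dates following the first administration of study drug or that worsen following the first administration of study drug". No closing date is given. The schedule footnote in SAP 5.1 runs AE collection from when the parent or guardian "signs informed consent until the last study visit", which is Visit 8 (Day 90 ±14). SAP 5.9 places the last dose on the day before Visit 6 (Day 28 ±7), and SAP 5.1 says "No study drug doses were delivered after Visit 6".

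**The concern.** A safety endpoint is named, but no AE section says how it will be tabulated. The other by-visit safety and tolerability endpoints are carried through: biomicroscopy, IOP and photophobia are each summarized by visit in SAP 10.4.3, and biomicroscopy and IOP also as the worst case on treatment. Only AEs lose their time dimension, which looks more like an omission than a choice.

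The comparison of safety is part of the primary objective (SAP 4). As planned, AEs would be compared only through counts pooled from first dose to study exit. For a completer, most of that time is after the drug has stopped. If the two steroids differ in AEs only while they are being given, a reader of the pooled table could miss it.

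**Working it through.** **Check of the plan's own timing figure.** The documents state no AE rate and no length for the off-drug period. The nearest stated figure is the study duration of 11 to 19 weeks. With Visit 8 at Day 90 ±14 and screening 1 to 29 days before surgery:

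- shortest: (90 − 14 + 1)/7 = 11.0 weeks
- longest: (90 + 14 + 29)/7 = 19.0 weeks

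The figure reproduces, so the visit windows can be relied on.

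**Off-drug days for a completer.** Visit 6 falls on Day 21 to 35, so the last dose falls on Day 20 to 34 (nominally Day 27). Visit 8 falls on Day 76 to 104.

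- nominal: 90 − 27 = 63 days, and 63/90 = 70% of the postoperative days
- smallest: 76 − 34 = 42 days
- largest: 104 − 20 = 84 days

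Subjects who are rescued stop study drug and exit (protocol 3.2.3), so these figures do not apply to them.

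**Effect of pooling when the difference is confined to dosing.** Let p be a subject's on-drug risk of an event and b the off-drug risk, equal in both arms and independent of what happened on drug. The risk to Day 90 is 1 − (1 − p)(1 − b). The difference between arms is therefore (p₂ − p₁)(1 − b).

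Assumed on-drug risks are 10% and 20%, and b is varied because the documents give no value:

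| b | Lower arm | Higher arm | Difference (points) | Risk ratio |
|---|---|---|---|---|
| 0% (on drug only) | 10% | 20% | 10 | 2.00 |
| 10% | 1 − 0.9×0.9 = 19% | 1 − 0.8×0.9 = 28% | 9 | 1.47 |
| 20% | 1 − 0.9×0.8 = 28% | 1 − 0.8×0.8 = 36% | 8 | 1.29 |
| 30% | 1 − 0.9×0.7 = 37% | 1 − 0.8×0.7 = 44% | 7 | 1.19 |
| 40% | 1 − 0.9×0.6 = 46% | 1 − 0.8×0.6 = 52% | 6 | 1.13 |

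**Effect of pooling when the difference persists.** If the off-drug risks are also 10% and 20%, the totals are 1 − 0.9×0.9 = 19% and 1 − 0.8×0.8 = 36%. The difference grows to 17 points and the risk ratio is 36/19 = 1.89. Pooling does not hide such an effect on the difference scale.

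**The case against.** Several points on the other side have weight.

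- SAP 6 says that analyses will generally be summarized by treatment group, or by group and scheduled time point, as appropriate. That permits by-visit AE tables, so a reader who infers that the endpoint will certainly go unreported goes too far. But the clause names no AE table, interval or denominator, and no AE section takes it up.
- SAP 10.4.1.6 gives time to onset. This covers only related TEAEs, in a listing, and gives no incidence by visit.
- A reader might infer that the off-drug days dilute every AE difference. The documents do not support this. It holds only for effects confined to dosing with similar later risk in both arms; the last calculation under the working shows the opposite for a persisting effect.
- A reader might also take 70% as the amount of dilution. It is a share of days, and nothing in the documents says how AEs are spread over time.
- No hypothesis test is planned for AEs, so no formal comparison loses power. IOP and biomicroscopy are partly protected by their own by-visit and on-treatment summaries.
- A full-period count is the right output for the overall incidence endpoint, and an open-ended TEAE window agrees with the stated collection period.

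What stands after all this is the listed endpoint with no specified table, and an AE comparison with no view of the dosing period.

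**Conclusion.** The point holds as an inconsistency with a modest consequence. AE type and incidence by visit is listed in both documents, and neither specifies a table that would report it. The pooled TEAE tables combine dosing with a nominal 63 off-drug days (42 to 84) for a completer.

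Whether this masks anything depends on facts the documents do not give. Under the assumed 10% and 20% on-drug risks and a common later risk of 10% to 40%, a 10-point difference would appear as 9 to 6 points. Those rates are illustrative, and the result requires an effect limited to dosing.

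Early exit adds a smaller problem. If rescue differs between arms, AE observation time differs too, and percentages of the Safety population do not show it. The harm is to descriptive interpretation; the primary efficacy conclusion is unaffected.

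**What to change.** In SAP 10.4.1.1, for ocular events in the study eye and for non-ocular events, add:

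1. TEAE tables by onset interval between scheduled visits. This is what reports the listed endpoint.
2. TEAE tables on treatment (first dose to recorded last dose) and after treatment (to study exit). This split alone would not report AEs by visit, so it supplements the first item.

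Use the number of subjects still in the study at the start of each interval as the denominator. Keep the full-period table with Safety-population denominators beside them.

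Use the recorded last-dose date, which SAP 9.2.1 already needs for exposure, to close the on-treatment period. SAP 5.9 runs the taper until Day 28 but puts the last dose on the day before Visit 6, itself a movable visit. Those statements must be reconciled so that the end of treatment is unambiguous. SAP 10.4.3 also refers to the worst case on treatment without defining the term, and one definition could serve both.

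The cost is SAP wording and one extra table set. AE start dates are already collected, and SAP 10.4.1 has a rule for incomplete ones. The downsides are smaller counts per cell and denominators that differ from those in the other AE tables, which a footnote should state.

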5.2.4 Tolerability Endpoints

The tolerability endpoint is as follows:

- Ocular symptoms (photophobia) at each visit

5.3 Statistical Hypotheses

The test for the non-inferiority of LE Ophthalmic Gel, 0.5% to Prednisolone Acetate Ophthalmic Suspension, 1% will be based on the following one-sided null hypothesis (H_0) and alternative hypothesis (H_a):

$$H_0: \mu_{LE} - \mu_{PR} \geq 0.35 \text{ versus } H_a: \mu_{LE} - \mu_{PR} < 0.35,$$

where μ_{LE} and μ_{PR} are the mean grade of ACI at Visit 5 (Postoperative Day 14) for LE Ophthalmic Gel, 0.5% and Prednisolone Acetate Ophthalmic Suspension, 1% treatment groups, respectively.

5.4 Sample Size

The planned sample size of 120 completed subjects (60 subjects per treatment group) yields 98% power to detect non-inferiority of LE Ophthalmic Gel, 0.5% to Prednisolone Acetate Ophthalmic Suspension, 1%. This sample size assumes a common standard deviation of 0.47, a two-sided alpha=0.05, a non-inferiority margin of 0.35 and an expected difference of 0 for the difference in means between treatment groups using ACI at Visit 5 (Postoperative Day 14). Assuming a subject dropout rate (including the initiation of rescue medication) of 12%, approximately 140 subjects will be randomized, of which at least 60 subjects will be in the age group 0-3 years as per the FDA's Written Request.

The power and sample size calculations were done using nQuery Advisor version 7.0.

5.5 Randomization and Masking

A total of approximately 140 subjects from ages 0-11 will be randomized at Visit 2 (Day 0 to receive LE Ophthalmic Gel, 0.5% or Prednisolone Acetate Ophthalmic Suspension, 1% in a 1:1 ratio. The subgroup age 0-3 years will consist of at least 60 subjects.

The final randomization list will be created prior to study enrollment by an unmasked statistician not otherwise involved in the trial. Each randomization number will correspond to a treatment group assignment. The Investigator and Sponsor personnel involved in the conduct of the study will be fully masked to the study medication. Designees at each study site will be able to view both test and comparator bottles and are therefore considered unmasked, although they will not have access to the randomization codes.

The randomization code can be broken in an emergency situation before the database lock where knowledge of the study treatment is critical to subject safety.

5.6 Study Sample

Approximately 140 subjects will be enrolled in this double-masked, parallel-group, active-controlled study at approximately 30 investigative sites in the United States (US), European Union (EU), and Asia Pacific (AP).

5.6.1 Inclusion Criteria

Subjects must meet all the inclusion criteria listed in Section 3.2.1.1 of the clinical trial protocol.

5.6.2 Exclusion Criteria

Subjects have to meet (ie, respond “NO” to) all the exclusion criteria listed in Section 3.2.1.2 of the clinical trial protocol.

5.7 Procedures for Discontinuing Treatment and Removal of Subjects from Study

A subject CAN be discontinued (at the discretion of the Investigator, the Sponsor, and/or the Institutional Review Board/Ethics Committee) prior to the final study visit for any of several reasons, including, but not limited to:

- A serious adverse event (SAE) occurring during the course of the study, which precludes continued treatment or follow-up
- The subject’s parent/legally authorized representative not following required study procedures

A subject HAS TO be discontinued prior to the final study visit for any of the following reasons:

- Voluntary withdrawal
- Onset of menarche during the study
- Death
- Investigator decision that it is not in the best medical interest of the subject to continue participation in the investigation
- Requires rescue medication

Adverse events and reasons for withdrawal and discontinuation will be documented appropriately according to the protocol. The assessments scheduled for Visit 8 (Postoperative Day 90) should be performed at this early termination visit. Any randomized subject discontinued from the study will not be replaced.

5.8 Test Article/Comparator Product

Loteprednol Etabonate Ophthalmic Gel, 0.5%, contains the active ingredient loteprednol etabonate 0.5% and the preservative benzalkonium chloride (BAK), 0.003%. It also contains the inactive ingredients glycerin, propylene glycol, sodium chloride,

polycarbophil, sodium hydroxide, tyloxapol, edetate disodium dihydrate, boric acid, and water for injection.

Prednisolone Acetate Ophthalmic Suspension, 1% contains the active ingredient prednisolone acetate 1% and the preservative BAK, 0.004%. It also contains the inactive ingredients boric acid, edetate disodium, hypromellose, polysorbate 80, purified water, sodium bisulfite, sodium chloride, and sodium citrate. The pH during its shelf life ranges from 5.0 - 6.0.

5.8.1 Selection and Timing of Dose

The subject will receive the first dose of study drug by the unmasked designee at the end of the surgery. Either the unmasked designee or the subject's parent/legal guardian will then administer 1 to 2 drops of study drug to the lower cul-de-sac of the study eye once in the evening on the day of surgery and then QID, at approximately 4 hour intervals, beginning on the morning after surgery. QID dosing will continue until postoperative day 14, including dosing at appropriate time intervals on the day of a visit. Dosing of both test articles was subsequently adjusted as described in Section 5.9.

5.9 Dose Adjustment/Modifications

Treatment will be tapered from QID to BID during the interval between postoperative days 15 and 21. Treatment will be further tapered to QD from postoperative day 22 until day 28, with the last dose being administered on the day prior to Visit 6 (Postoperative Day 28).

5.10 Treatment Compliance Follow-up

In order to assess compliance of treatment administration, subject/subject's parent/legal guardian will be instructed to record the date and time of each study drug administration on a diary provided by the Sponsor.

6 General Statistical Considerations

All statistical analyses will be conducted using SAS Version 9.4 or higher.

Continuous data will be summarized using descriptive statistics: n, mean, standard deviation, median, minimum, and maximum. Means and medians will be presented to 1 more decimal place than the recorded data. Standard deviations will be presented to 2 more decimal places than the recorded data. Minimum and maximum values will be presented using the same number of decimal places as the recorded data. Categorical data will be summarized using counts for each category and corresponding percentages. Percentages will be presented to 1 decimal place. Confidence intervals will be presented using the same number of decimal places as the parameter (i.e. mean).

All statistical analyses will generally include summaries by treatment group or by treatment group and scheduled time point, as appropriate.

In general, the baseline value for a variable is defined as the last observation prior to the first dose of double masked study medication (Day 0), including the screening value, if necessary.

Study Day 0 is defined as the date on which a subject was randomized and took the first dose of double masked study medication. Other study days are defined relative to the Study Day 0 as Dose Date – Day 0 date + 1. The visit window for Day 7 is ± 2 , for Day 14 is ± 3 , for Day 28, 42, is ± 7 , and for Day 90 is ± 14 .

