The purpose of this statistical analysis plan (SAP) is to ensure the credibility of the study findings by specifying the statistical approaches to the analysis of the data prior to database lock. This SAP covers the planned analyses of all data collected on the eCRFs, and will identify handling of data issues. The statistical analysis plan presented in this document will supersede the statistical analysis methods described in the clinical protocol. Any deviations/changes from the planned analyses described in this SAP will be identified, with justification, in the appropriate section of the clinical study report. This SAP is based on the final Protocol Study #670, amendment 6, dated 22 May, 2013 and on Administrative Change Memo 1, dated 19 Aug 2013.

4 **Study Objective**

The primary study objective is to compare the efficacy and safety of Loteprednol Etabonate (LE) Ophthalmic Gel, 0.5% to Prednisolone Acetate Ophthalmic Suspension, 1% for the treatment of postoperative inflammation following ocular surgery for childhood cataract.

5 **Study Methods**

5.1 **Study Design**

This study is a randomized, double-masked, parallel-group, active-controlled, multicenter study involving approximately 10 investigative sites in the United States (US), European Union (EU), and Asia Pacific (AP).

A total of 140 subjects aged 0-11 years will be randomized in a 1:1 ratio to LE Ophthalmic Gel, 0.5% or Prednisolone Acetate Ophthalmic Suspension, 1%. Of the 140 randomized subjects, at least 60 subjects (approximately 30 subjects per treatment group) will be in the age range from 0-3 years. Prednisolone Acetate Ophthalmic Suspension, 1% was chosen as the active-control because it has a long history as the standard of care for pediatric cataract surgeries in the US.

Study duration will be approximately 11-19 weeks from screening to the last visit (Visit 8, Postoperative Day 90). Subjects will visit the clinic eight times. Visit 1 will be the Screening Visit and will occur up to a maximum of 29 days prior to surgery. Visit 2 will be on the day of surgery. At the end of surgery on Visit 2, eligibility for randomization into the study will be assessed and, if appropriate, subjects will be randomized at this time. Randomized subjects will complete postoperative study Visits 3 through 8 (Postoperative Days 1, 7, 14, 28, 42, and 90, respectively).

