9.2.2 Treatment Compliance

Study drug compliance will be calculated for each subject by taking into account whether a subject takes all doses of study drug as instructed. Compliance will be based solely on the subject diaries. The study drug compliance rate will be presented overall, at Visit 4, Visit 5 and Visit 6. The study drug compliance rate for Visit 5 will be calculated by dividing the total number of dosing recorded in the diary for the subject for that period by the total number of days times 4 and then multiplying by 100. The first day of dosing will be ignored entirely, since subjects may be compliant with any number of doses.

The overall study drug compliance rate will be calculated by dividing the total number of dosing recorded in the diary for a subject across the entire treatment period by the total number of days times 4 for days \leq 14, times 2 for days between days 15 and 21 and times 1 for days between 22 and 28 and then multiplying by 100. The first day of dosing will be ignored entirely, since subjects may be compliant with any number of doses. The number and percentage of subjects in each of the following compliance rate categories will also be reported: (\leq 50%, 51-60%, 61-70%, 71-80%, 81-120%, and $>$ 120%). Percentages will be calculated out of the number of subjects who returned diaries from that dosing period. The number and percentage of subjects in each compliance rate category will be presented overall, at Visit 4, Visit 5 and Visit 6.

10 Statistical Analyses

All efficacy analyses will use a 2-sided alpha = 0.05 test unless otherwise stated. No adjustments will be made for multiplicity testing.

Analyses will be performed on the ITT and PP analysis set for both the primary efficacy endpoint and secondary efficacy endpoints. The safety analyses will be performed on the SAF.

All continuous efficacy endpoints will be summarized graphically by treatment group displaying the mean and corresponding standard errors at each time point for the primary efficacy endpoint or line graphs of the continuous secondary efficacy endpoints over scheduled time.

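### SAP section 6 puts Study Day 0 at surgery but adds 1 to every other day, so postoperative Day 14 computes as Study Day 15 (minor)

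*SAP*

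**What the plan says.** SAP section 6 (General Statistical Considerations) sets the anchor: "Study Day 0 is defined as the date on which a subject was randomized and took the first dose of double masked study medication". The next sentence gives the rule for all other days: "Other study days are defined relative to the Study Day 0 as Dose Date – Day 0 date + 1". The sentence after that lists the visit windows for Days 7, 14, 28, 42 and 90, with no separate clock for them.

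The schedule in SAP section 5.1 puts surgery at Day 0, Visit 3 at Day 1 and Visit 5, the primary endpoint visit, at Day 14 (±3 days). Footnote 3 to the schedule fixes the count: "Visit 3 (postoperative day 1) should occur on the next calendar day post-surgery". Screening is at Day -15 (±14 days), and footnote 2 adds: "Screening and surgery cannot take place on the same day".

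The regimen is also in postoperative days. SAP 5.8.1: "QID dosing will continue until postoperative day 14, including dosing at appropriate time intervals on the day of a visit". SAP 5.9: "Treatment will be tapered from QID to BID during the interval between postoperative days 15 and 21". The overall compliance rate in SAP 9.2.2 uses the same cut-points: its denominator multiplies by 4 up to day 14, then "times 2 for days between days 15 and 21 and times 1 for days between 22 and 28". It does not say which clock those days are on.

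SAP section 3 gives these rules priority over the protocol: "The statistical analysis plan presented in this document will supersede the statistical analysis methods described in the clinical protocol".

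**The concern.** The two sentences in section 6 do not fit together. Applied to the anchor date itself, the formula returns 1, yet that date has just been named Study Day 0. Every later date then carries a number one higher than its postoperative day, in conflict with the SAP's own schedule.

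This is the only study-day formula in the SAP, and the SAP overrides the protocol's statistical methods, so a programmer has no competing rule to fall back on. The visit windows come in the very next sentence with bare day numbers, and section 9.2.2 also uses bare day numbers. The listings of time to onset for related adverse events (10.4.1.6) and of days on study for deaths (10.4.1.7) have no day rule of their own and could inherit the error.

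At stake are study-day labels, flags for out-of-window visits, and the compliance percentages. The efficacy estimates are not at stake.

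**Working it through.** **Inputs.** Day 0 is the date of randomization and first dose (SAP 6). The first dose is given at the end of surgery (SAP 5.8.1), so Day 0 is the surgery date. Scheduled days and windows are from SAP 5.1 and SAP 6. The multipliers 4, 2 and 1 and the exclusion of the first dosing day are from SAP 9.2.2. The last dose falls on the day before Visit 6, nominally postoperative Day 27 (SAP 5.9).

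**Step 1: day numbers.** For postoperative day d, the SAP formula gives d + 1. Without the added 1 it gives d.

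| Postoperative day | SAP formula | Without the + 1 | SAP schedule |
|---|---|---|---|
| -15 | -14 | -15 | Day -15 (screening target) |
| -1 | 0 | -1 | within the screening window |
| 1 | 2 | 1 | Day 1 |
| 7 | 8 | 7 | Day 7 |
| 14 | 15 | 14 | Day 14 |
| 28 | 29 | 28 | Day 28 |
| 42 | 43 | 42 | Day 42 |
| 90 | 91 | 90 | Day 90 |

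The formula as written reproduces none of the scheduled days. Without the added 1, all of them are reproduced. Under the formula no date is Study Day 1. If it is extended to dates before surgery, the day before surgery also becomes 0. A screening visit on that day, which the window allows, would then share its label with surgery.

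**Step 2: visit windows, if the formula is extended to visit dates.** A window of Study Days a to b corresponds to postoperative days a - 1 to b - 1.

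| Visit | Window | Intended postoperative days | Accepted under the formula |
|---|---|---|---|
| 4 | 7 ± 2 | 5-9 | 4-8 |
| 5 | 14 ± 3 | 11-17 | 10-16 |
| 6 | 28 ± 7 | 21-35 | 20-34 |
| 7 | 42 ± 7 | 35-49 | 34-48 |
| 8 | 90 ± 14 | 76-104 | 75-103 |

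**Step 3: overall compliance denominator, if the formula supplies the days in 9.2.2.** Nominal dosing runs over postoperative Days 1-27.

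- Postoperative clock: 14 × 4 + 7 × 2 + 6 × 1 = 56 + 14 + 6 = 76.
- SAP formula (Study Days 2-28): 13 × 4 + 7 × 2 + 7 × 1 = 52 + 14 + 7 = 73.
- The gap of 3 doses comes from postoperative Day 14 (counted as 2 instead of 4) and Day 21 (counted as 1 instead of 2).
- Full adherence: 76/76 = 100.0% against 76/73 = 104.1%. Both fall in the 81-120% category.
- A child with 60 recorded doses: 60/76 = 78.9% (71-80% category) against 60/73 = 82.2% (81-120% category).

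The figures 76 and 73 are nominal. Visit 6 has a window of ±7 days, so individual denominators will vary.

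**The case against.** The strongest reply is that nothing in the SAP is expressly computed from Study Day. Summaries are by scheduled time point, efficacy and most safety data are by visit, and extent of exposure has its own rule from first to last dose. Protocol 5.1.9 keeps out-of-window visits on the form for the scheduled visit. The formula names dose dates only, so a strictly literal reading shifts no visit window. This is plainest for Visits 7 and 8, which come after dosing has ended. The shared label for the day before surgery needs the formula to be applied before any dose exists, and footnote 2 governs the conduct of visits, not labels. The Visit 5 compliance rate uses a count of days times 4, which a uniform shift leaves alone. Nothing ties the two listings to the formula.

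Most of this stands as a limit on the consequences. The window, screening and listing effects need an extension of the formula and are not shown to occur. Any effect on per-protocol membership would need window deviations to be judged from the derived day, which the SAP does not say.

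Two things remain. The contradiction between the Day 0 anchor and the added 1 is in the text and is not repaired anywhere else. And the overall compliance rate in 9.2.2 counts doses by day, which is where a dose-date formula applies most naturally. There a reported category can change, as the 60-dose example shows. That the formula gives no rule for assessment dates is a further reason to rewrite it.

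**Conclusion.** The concern holds as a minor derivation error. As written, every dose date after surgery carries a study day one higher than its postoperative day, against the SAP's own schedule. The intended clock is clear from the schedule and the regimen text, so the formula is wrong and the windows and dosing periods are not.

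The downstream effects are conditional. If the formula is programmed into 9.2.2, the nominal compliance denominator is 73 instead of 76, which inflates rates by a factor of 76/73 (about 4%) and can move a child near a cut-point up one category. If it is extended to visit dates, out-of-window flags shift by one day. The by-visit efficacy estimates do not change. This assumes that visits are analysed as recorded on the scheduled form and that any day-numbered rule touching efficacy, such as the Day 14 rescue cut-off in SAP 6.2, is read in postoperative days.

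**What to change.** In SAP section 6, replace the formula with: Study Day = assessment, event or dose date minus Day 0 date, with nothing added. Study Day then equals postoperative day, the day after surgery is Day 1, and dates before surgery are negative. Add one sentence stating that the section 6 visit windows and the section 9.2.2 dosing periods use this clock. The listings in 10.4.1.6 and 10.4.1.7 should refer to the same rule or give their own.

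The cost is a short SAP correction and the matching change to the derivation program. Data collection, visit conduct and the dosing regimen are untouched.
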